--	---

	
c. Contact with infected individuals at work or at home d. Use of community care
 
Describe the incidence of Covid-19 infections among patients and healthcare personnel.
 
Compare the distribution of contamination risk factors among patients and those of the general population (Constances cohort).
 
Describe adherence to SARS-CoV-2 vaccination among personnel and patients.
 
WP 5 : PSYCHOLOGY OPTIONAL FOR CENTERS
 
Examine the evolution of state anxiety over time and determine whether perceptions of anxiety evolve, indicating a possible adaptation process.
 
Examine associations between post-traumatic growth, trait anxiety, sociodemographic variables, and the evolution of state anxiety over time.
 
Examine the evolution of depression over time and determine whether perceptions of depression evolve, indicating a possible adaptation process.
 
Examine associations between post-traumatic growth, trait anxiety, sociodemographic variables, and the evolution of depression over time.

INCLUSION CRITERIA:	
 1) Age \geq 18 years; 2) Population from a CLCC meeting one of the following three definitions: 
  patients undergoing treatment,  patients in follow-up (having completed their treatment more than one year prior to inclusion),  healthcare personnel; 3) Subjects having had or not had an infection compatible with, or confirmed as, Covid-19; 4) Subjects informed and having signed the informed consent form; 5) Subject affiliated with a social security system.
NON-INCLUSION CRITERIA:	
 1) Refusal to provide consent; 2) Patients unable to give consent or presenting psychiatric history; 3) Inability to comply with medical follow-up for geographical, social, or psychological reasons; 4) Individuals under legal protection (guardianship or curatorship); 5) Individuals deprived of liberty by judicial or administrative decision.
PRIMARY EVALUATION CRITERION:	
Biological data: Serological status (rapid immunochromatographic test) and IgM and IgG titers (enzyme immunoassay, ELISA type), performed at M0, M3, M6, M9, and M12. Collection via questionnaire of results from tests detecting SARS-CoV-2 viral genome (RT-PCR molecular test) performed in community settings
 
Clinical data: Follow-up questionnaire on clinical signs suggestive of Covid-19.

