COMPLETION EVALUATION CRITERION:	
WP 1: SEROLOGY MANDATORY
 
Time to appearance and titers of anti-SARS-CoV-2 IgM and IgG at the different measurement timepoints in each subgroup. Specificity, sensitivity, PPV (Positive Predictive Value), and NPV (Negative Predictive Value) from the different tests, with quantitative serology (ELISA) considered the gold standard.
 
IgG levels at M12.
 
Number of reinfections or viral reactivations (appearance of clinical signs confirmed by RNA tests — RT-PCR positive — and serology) in the subgroup of patients who developed IgG.
 
Anti-SARS-CoV-2 IgG titers according to the occurrence or absence of reinfection during follow-up.

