	
Time to appearance and titers of anti-SARS-CoV-2 antibodies according to FCGR2A and FCGR3A genotypes.
 
IgG-positive results on rapid TROD tests and semi-quantitative ELISA IgG titers in vaccinated individuals.
 
Number of vaccinated individuals in whom anti-Spike protein IgG titration is feasible.
 
Number of vaccinated individuals with positive neutralization test results.
 
WP 2: CLINICAL MANDATORY
 
Number of Covid-19-related deaths, severe infections (requiring oxygen therapy), prolonged symptomatic infections, moderate infections, and asymptomatic infections, relative to all subjects in the population with seropositivity and/or a positive RT-PCR test, as well as duration of the symptomatic phase.
 
Reinfection cases are defined as recurrence of clinical symptoms and/or positive viral PCR and/or positive IgM serology after a symptom-free interval. Frequency is defined as the number of reinfection cases relative to all subjects in the population with seropositivity and/or a positive RT-PCR test.
 
Among subjects in the population with seropositivity and/or a positive RT-PCR test, factors significantly associated with severe forms / mortality among the following:
 
 ○ Ongoing or recent anticancer treatment: 
 - Immunotherapy - Chemotherapy, according to frequency of grade 3/4 neutropenia and/or lymphopenia - Radiotherapy - Surgery ○ Concomitant treatments ○ Comorbidities ○ Cancer (cancer type, stage, etc.) ○ Cancer-related medical history (number of treatment lines, surgical and medical history) ○ Biological markers (CRP, etc.) 
WP 3: ECONOMIC ANALYSIS OPTIONAL FOR CENTERS
 
Type of organizational and practice changes implemented and their frequency according to specialties/services.
 
Total number of patients affected and number of patients per type of change.
 
Positive or negative effects on patient morbidity or mortality.
 
Monetary value of resources mobilized (increased or decreased) depending on observed changes.
 
Number and duration of healthcare personnel sick leave.
 
Benefits of organizational changes for healthcare personnel.
 
Costs of systematic screening of patients and healthcare personnel..
 
WP 4 : PUBLIC HEALTH / EPIDEMIOLOGY OPTIONAL FOR CENTERS
 
Number of SARS-CoV-2 infections among all monitored patients.
 
Prevalence of SARS-CoV-2 infection/immunization during the 3 weeks following the end of lockdown among patients, healthcare personnel working onsite, and healthcare personnel who were confined, by age group, by region (center), and according to comorbidities.
 
Number of SARS-CoV-2 infections among all monitored healthcare personnel.
 
Quarterly incidence rates among patients and healthcare personnel by age group, by region (center), and according to comorbidities.
 
Percentages (qualitative variables) / means or medians (quantitative variables).

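### The three WP 2 analysis sets accept any seropositivity as infection, with no vaccination limit, although the protocol plans to record IgG in vaccinated participants

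*Protocol*

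**What the plan says.** All references are to the protocol synopsis; the statistical analysis plan was not available.

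In section D, Completion evaluation criterion, WP 2, three sets rest on the same condition:

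- Severity: deaths, severe, prolonged, moderate and asymptomatic infections are counted "relative to all subjects in the population with seropositivity and/or a positive RT-PCR test, as well as duration of the symptomatic phase".
- Reinfection: "Frequency is defined as the number of reinfection cases relative to all subjects in the population with seropositivity and/or a positive RT-PCR test".
- Risk factors: "Among subjects in the population with seropositivity and/or a positive RT-PCR test, factors significantly associated with severe forms / mortality".

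Because of the and/or, seropositivity alone is enough. No antibody class, antigen, sampling date or vaccination condition is attached to it there or elsewhere in the document.

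The Primary evaluation criterion says how serology is obtained: "Serological status (rapid immunochromatographic test) and IgM and IgG titers (enzyme immunoassay, ELISA type), performed at M0, M3, M6, M9, and M12".

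The WP 1 secondary objectives include following IgG after vaccination and counting those who then have antibodies. The matching WP 1 criteria are "IgG-positive results on rapid TROD tests and semi-quantitative ELISA IgG titers in vaccinated individuals" and "Number of vaccinated individuals in whom anti-Spike protein IgG titration is feasible". Spike is the only antigen named in the document, and only for that titration in vaccinated people.

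**The concern.** The condition that stands for infection in WP 2 can also be met through vaccination, on test types that the protocol itself applies to vaccinated participants. A vaccinated subject who was never infected and has no symptoms but is IgG-positive meets the WP 2 condition as written. The only severity category open to that subject is asymptomatic infection.

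WP 2 is mandatory for centers. Its objectives describe severity separately in personnel, follow-up patients and patients under treatment, and within the last group by chemotherapy and immunotherapy. Extra uninfected subjects lower the severe and fatal shares in every group, and lower them most where vaccine uptake or IgG response is highest. A difference in severity between groups could then reflect vaccination alone. The risk-factor analysis would partly contrast severe cases with people who never had the disease.

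**Working it through.** **Plan's own figure.** 12,000 patients + 3,000 healthcare personnel = 15,000, as stated. This is a recruitment estimate without a power calculation, and the point does not depend on it.

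**Inputs.** The protocol gives no infection rate, vaccine coverage, post-vaccination IgG positivity or severe share. All values below are assumed:

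- p = share truly infected
- v = share vaccinated, independent of infection
- s = share of the vaccinated who test IgG-positive on the routine tests
- true severe share among the infected = 10%

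**Formulas.** Share of the cohort in the WP 2 set: a = p + (1 − p)·v·s. Uninfected share of the set: (a − p)/a. Severe share as read: 0.10·p/a. If the tests do not react to vaccine antibody, s = 0, a = p, and there is no error.

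**Dilution, with p = 0.10 and s = 0.60.**

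| v | a | uninfected share of set | severe share as read |
|---|---|---|---|
| 0.10 | 0.10 + 0.90 × 0.06 = 0.154 | 0.054/0.154 = 35% | 0.010/0.154 = 6.5% |
| 0.20 | 0.10 + 0.90 × 0.12 = 0.208 | 0.108/0.208 = 52% | 0.010/0.208 = 4.8% |
| 0.50 | 0.10 + 0.90 × 0.30 = 0.370 | 0.270/0.370 = 73% | 0.010/0.370 = 2.7% |

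In the last row, a true asymptomatic share of 30% (assumed) would read (0.03 + 0.27)/0.37 = 81%.

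**Wider range.** With p from 5% to 20%, v from 10% to 80% and s from 70% to 95%, the uninfected share of the set runs from 22% to 94%, and the 10% severe share reads between 7.8% and 0.65%.

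**Incomplete detection.** Suppose all severe but only 70% of non-severe infections are detected (p = 0.10, v = 0.50, s = 0.60).

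- Detected infections: 0.010 + 0.090 × 0.7 = 0.073.
- Set: 0.073 + 0.027 × 0.3 + 0.90 × 0.3 = 0.3511.
- Uninfected share: 0.270/0.3511 = 77%.
- Severe share as read: 0.010/0.3511 = 2.8%, against 0.010/0.073 = 13.7% among detected infections.

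**Spurious contrast.** Take two groups alike except for IgG response to vaccine, 60% against 90%. The ratio of their severe shares is a(s = 0.9)/a(s = 0.6):

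- p = 0.20, v = 0.10: 0.272/0.248 = 1.10
- p = 0.05, v = 0.80: 0.734/0.506 = 1.45

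These are the extremes for p from 5% to 20% and v from 10% to 80%.

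**The case against.** The strongest objection is that the harm depends on a fact the document does not give. The antigen of the routine rapid test and ELISA is not stated. Moreover, the routine ELISA is called quantitative, while the one listed for vaccinated individuals is called semi-quantitative and is joined by a separate anti-Spike titration. A different assay for vaccinated subjects is therefore possible. This stands to the extent that the point must be conditional. It does not dispose of it: the IgG-positive rapid test is itself a criterion in vaccinated individuals, and nowhere are the routine tests said to be infection-specific.

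A second objection is that a statistical analysis plan could define seropositivity as infection-related. It could, but the protocol has already fixed the denominators, and a plan that follows them literally carries the problem forward.

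Four stronger readings are tempting, and the document does not support them.

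- *That IgM in the reinfection definition is also contaminated.* The WP 2 numerator reads: "Reinfection cases are defined as recurrence of clinical symptoms and/or positive viral PCR and/or positive IgM serology after a symptom-free interval". No passage says that vaccination produces positive IgM on these tests.
- *That WP 1 would count first infections after vaccination as reinfections.* Its base is indeed loosely put, "in the subgroup of patients who developed IgG", but the event must be confirmed by RT-PCR and serology, and reinfection presupposes an earlier infection. Only a clarification of the base is warranted.
- *That WP 2 reinfection frequency must be understated.* The denominator is enlarged, but the numerator accepts recurring symptoms alone, so the net direction is undetermined.
- *That the illustrations estimate the actual bias.* Every input is assumed. They show direction and what could happen, not size.

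**Conclusion.** The point holds in conditional form. The three WP 2 sets are fixed without a vaccination limit in a protocol that plans to record IgG on rapid test and ELISA in vaccinated participants. As written, the rule admits vaccinated, never-infected, IgG-positive subjects as infections unless the routine tests do not react to vaccine antibody. If they do react, severe and fatal shares are too low, the asymptomatic share is too high, and comparisons between groups can mislead. This is a stated rule that yields a wrong set, not a detail left open.

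The size cannot be derived from the document. It ranges from nil, with an infection-specific assay, to a severe share read at about a quarter of its true value in the assumed case of 10% infected, 50% vaccinated and 60% IgG response. The wording should be corrected. The remainder of WP 1 and the data collection are not called into question.

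**What to change.** In the three WP 2 sets, count a subject as infected on any one of:

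1. a positive RT-PCR at any time;
2. seropositivity in a sample taken before the first vaccine dose;
3. after vaccination, seropositivity only on an antibody that vaccination does not induce, if that test is run on the frozen samples.

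If the routine tests are already infection-specific, say so instead. Report vaccinated subjects who are seropositive without such evidence in a separate line. Do not censor follow-up at the first dose. Leave the WP 1 vaccination objectives and the IgM element of the reinfection definition unchanged. For the WP 1 reinfection count, add only that the base means IgG from infection.

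**Cost in data.** Vaccination dates relative to samples are needed in all centers. WP 1 implies vaccination status, but dates are not mentioned, and vaccination adherence belongs to WP 4, which is optional.

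**Cost in missed infections.** Unless limb 3 is run, infections without RT-PCR are missed after the dose, and between the last pre-dose sample (quarterly, plus on demand for symptoms) and the dose. Nothing in the eligibility criteria excludes people vaccinated before M0. They have no pre-dose study sample, so their earlier infections without RT-PCR are lost too. The infections found are skewed to symptomatic cases.

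An assumed illustration: v = 0.50, constant infection rate, all severe cases found by RT-PCR, and a share q of non-severe infections without RT-PCR. The missed share of non-severe infections is m, and a true 10% severe share reads 0.1/(0.1 + 0.9(1 − m)).

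- Doses uniform over 12 months (mean 6 months after the dose, mean gap 1.5 months, ignoring on-demand samples): m = 0.5·q·7.5/12. With q = 0.5, m = 0.156 and the share reads 11.6%. With q = 1, m = 0.3125 and it reads 13.9%.
- All vaccinated before M0, an upper bound: m = 0.5·q. With q = 0.5 it reads 12.9%, and with q = 1 it reads 18.2%.

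The present rule reads 2.7% with 10% infected and 60% IgG response. Because the remaining error also grows with vaccine uptake, severity should be shown by vaccination status at infection as a supplementary table.

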In a number of cases, the situation continues to worsen, with chest pain, respiratory discomfort, and a radiological pattern of viral pneumonia. Signs related to involvement of other organs have been described (neurological, dermatological, etc.).

This clinical picture may be severe enough to justify hospitalization in nearly 20% of symptomatic patients and admission to intensive care in 5% of these cases. These severe forms predominantly affect certain high-risk groups, particularly older and more fragile individuals, who represent the main cause of Covid-19-related deaths.

Clinical presentation and challenges

Initial descriptive studies came from China, but European and American data suggest differences. Incubation lasts about 5 days (range 2–12). Symptoms, when present, develop progressively: headache, muscle pain, fatigue, then fever and respiratory signs 2–3 days later. Some cases worsen with chest pain, dyspnea, and viral pneumonia. Multisystemic manifestations have been reported. Around 20% of symptomatic cases require hospitalization; 5% require ICU admission—mainly affecting elderly and fragile patients.

The main diagnostic test aims to detect viral RNA in nasal secretions or sputum, quantified by RT-PCR. This PCR test, which is rather uncomfortable, appears to have a substantial false-negative rate (~30%).

Screening for minimally symptomatic or asymptomatic forms — which are likely no less contagious — is essential to slow the pandemic and prevent overwhelming the healthcare system. At present, no systematic screening strategy has been implemented in France.

Numerous serological tests detecting IgG and IgM antibodies are emerging. They are much simpler and faster than RT-PCR.

While antibody production (IgM and/or IgG) is known to be detectable from the second week after symptom onset in the general population, recent studies report the appearance of IgM and IgG antibodies as early as the 4th day after onset of clinical signs.

However, the kinetics of IgM/IgG antibody production are poorly characterized in asymptomatic or mildly symptomatic individuals, and even less so in patients with pre-existing conditions (cancer or other causes of immunosuppression).

Finally, high IgG and IgM antibody titers appear to be independently associated with disease severity.

Covid and cancer

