	
Evaluate the neutralizing capacity of IgG (neutralization assays) after vaccination over the duration of the study.
 
WP 2: CLINICAL MANDATORY
 
Describe severity (asymptomatic, symptomatic, prolonged, severe, fatal) by age group:
 
 In healthcare personnel In cancer patients In patients in follow-up In patients undergoing treatment: 
 Receiving chemotherapy and according to whether the chemotherapy induces grade 3–4 neutropenia or lymphopenia (as defined in the primary literature) Receiving immunotherapy 
Determine the frequency of Covid-19 reinfection (recurrence of clinically suggestive symptoms with positive viral PCR and/or positive IgM serology) during follow-up in the different groups.
 
Identify risk factors (clinical and therapeutic) for developing severe forms of Covid-19 infection among patients.
 
WP 3: ECONOMIC ANALYSIS OPTIONAL FOR CENTERS
 
Describe the consequences of Covid-19 in terms of organizational changes and care practices, from the start of the epidemic until the end of systematic screening for patients and healthcare personnel.
 
Identify changes in healthcare personnel practices regarding:
 
Coordination between healthcare workers
 
 Communication Patient management 
Identify resources associated with organizational changes at the level of:
 
 Modification of treatment regimens for patients (e.g., chemotherapy, radiotherapy, surgery) Organization of teleconsultations Diagnostic investigations for new cancers 
Analyze the impact of changes on patient health status.
 
Evaluate resources allocated to:
 
 The organizational changes described above Systematic screening of patients and healthcare personnel Work stoppages. 
WP 4: PUBLIC HEALTH / EPIDEMIOLOGY OPTIONAL FOR CENTERS
 
Identify risk factors for SARS-CoV-2 infection among patients, including:
 
 Sociodemographic factors (age, socio-professional category, housing, cohabitation) Lifestyle (work modalities, mobility, protective measures, etc.) Contact with infected individuals at work or at home Care pathway in CLCCs (number and duration of visits, number of care units visited, etc.), use of community care 
Estimate SARS-CoV-2 infection prevalence at the end of the lockdown:
 
 among patients among healthcare personnel who continued onsite work among healthcare personnel who were confined 
Identify risk factors for Covid-19 infection among healthcare personnel, including:
 
 Sociodemographic factors (age, socio-professional category, housing, cohabitation) Lifestyle (work modalities, mobility, protective measures, etc.)

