--	--

	
Percentage of personnel and patients refusing vaccination, and distribution according to reasons for refusal.
 
WP 5 : PSYCHOLOGY OPTIONAL FOR CENTERS
 
a. and b. State anxiety score at 3, 6, 9, and 12 months. c. and d. Depression score at 3, 6, 9, and 12 months.
 
Variables assessed at T0 (before screening) State anxiety (STAI-State questionnaire, Spielberger, Gorsuch, Lushene, Vagg & Jacobs, 1983; 20 items) Post-traumatic growth (PTGI, Tedeschi & Calhoun, 1996; 21 items; induction instruction: "since the lockdown"). The PTGI evaluates perceived positive changes such as shifting life priorities, closer relationships with others, developing new interests, etc. Trait anxiety (STAI-Trait questionnaire, Spielberger et al., 1983; 20 items) Sociodemographic variables (related to the Epidemiology WP) Depression (HADS questionnaire, Zigmond & Snaith, 1983; 14 items)
 
At 3, 6, 9, and 12 months (within the week following screening) State anxiety (STAI-State, 20 items) Depression (HADS, 14 items)

--	---

E) DESCRIPTION OF THE STUDY INTERVENTIONS

In this study, screening of patients and healthcare personnel will be performed using two or even three techniques depending on the result:

- **Repeated blood sampling, performed at inclusion (M0), Month 3 (M3), Month 6 (M6), Month 9 (M9), Month 12 (M12), plus on demand in the event of Covid-19 symptoms:**
 - a) Rapid serological test (TDR) — qualitative
 - Performed immediately on site.
 - Technique: immunochromatography strip detecting IgM / IgG.
 - b) Serology by ELISA — quantitative
 - Performed later on frozen samples.
 - c) Genotyping of FCGR2A and FCGR3A genes
 - Performed only at M0.
- **Nasopharyngeal swab (RT-PCR)**
 Detection of viral RNA.

This examination is performed with immediate result exclusively in the event of symptoms, irrespective of the rapid test result, for patients hospitalized in a Covid unit when such a unit exists within the center.

Results of RT-PCR tests performed in community settings (outside the hospital) will be collected via questionnaires.

- **Questionnaires** (Linked to the Work Packages — some are therefore optional)
 - Patients : Q1, Q2, Q3
 - Healthcare personnel : Q1, Q2, Q3, Q4, STAI (ETAT & TRAI), PTGI, HADS

TRIAL SCHEDULE

INCLUSION PERIOD:	12 months
DURATION OF PARTICIPATION PER SUBJECT:	12 months
MINIMUM PARTICIPATION TIME PER PATIENT:	12 months
OVERALL STUDY DURATION:	24 months
START OF THE CLINICAL TRIAL:	June 2020

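### WP 2 gives two different case rules for the same reinfection frequency, and only the evaluation criterion lets symptoms without laboratory evidence count

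*Protocol*

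**What the plan says.** All of this stands in the protocol synopsis.

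- **Section D, Secondary objective, WP 2 (mandatory).** The frequency of reinfection is to be determined in the different groups, with reinfection explained in brackets as "recurrence of clinically suggestive symptoms with positive viral PCR and/or positive IgM serology".
- **Section D, Completion evaluation criterion, WP 2.** "Reinfection cases are defined as recurrence of clinical symptoms and/or positive viral PCR and/or positive IgM serology after a symptom-free interval". The next sentence sets the denominator: "Frequency is defined as the number of reinfection cases relative to all subjects in the population with seropositivity and/or a positive RT-PCR test".
- **Section D, Completion evaluation criterion, WP 1.** A separate count, "Number of reinfections or viral reactivations", needs clinical signs confirmed by a positive RT-PCR and by serology, and is taken "in the subgroup of patients who developed IgG".
- **Section E, study interventions.** Blood is drawn at the scheduled visits, "plus on demand in the event of Covid-19 symptoms". Study RT-PCR is done only when there are symptoms, for inpatients of a Covid unit where the centre has one. For other tests, "Results of RT-PCR tests performed in community settings (outside the hospital) will be collected via questionnaires".

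The protocol does not say which of the two WP 2 wordings takes precedence.

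**The concern.** An objective and the criterion that measures it should identify the same cases. Here the objective ties symptoms to a positive test, while the criterion lists symptoms, PCR and IgM as alternatives. A previously positive subject whose symptoms return, with no positive PCR or IgM, is a reinfection case under the criterion and not under the objective. The criterion also drops the requirement that the symptoms be suggestive of Covid-19. The Rationale names headache, muscle pain and fatigue as early symptoms, and these are not specific to the infection.

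Reinfection frequency by group is a stated objective of a mandatory work package. Two analysts who each follow the protocol faithfully could report different frequencies from the same data, and a reader could not tell from the protocol which one was meant.

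**Working it through.** The protocol gives no figure to reproduce here, so the check compares the two rules pattern by pattern. Let S = recurrent symptoms, P = positive PCR, I = positive IgM. The criterion is S or P or I. The objective reads naturally as S and (P or I); its grammar also allows (S and P) or I.

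| S | P | I | Objective, natural reading | Objective, alternative reading | Criterion |
|---|---|---|---|---|---|
| no | no | no | – | – | – |
| no | no | yes | – | case | case |
| no | yes | no | – | – | case |
| no | yes | yes | – | case | case |
| yes | no | no | – | – | case |
| yes | no | yes | case | case | case |
| yes | yes | no | case | case | case |
| yes | yes | yes | case | case | case |
| **Patterns counted** | | | **3** | **5** | **7** |

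1. On the natural reading the rules disagree on 7 − 3 = 4 patterns: symptoms only (1) and test-positive without symptoms (3).
2. On the alternative reading they disagree on 7 − 5 = 2 patterns: symptoms only and PCR only.
3. The symptom-only row differs on both readings. This does not depend on whether the word recurrence in the criterion governs symptoms alone or all three items.
4. Every pattern counted by the objective is also counted by the criterion. With the same N subjects in the denominator, criterion frequency − objective frequency = (subjects counted only by the criterion) / N ≥ 0. The symptom-free interval appears only in the criterion. It is set aside here because it could remove some cases from that side; it does not bring back the need for a test.
5. As a ratio, criterion / objective = 1 + (extra cases / objective cases). It reaches 2 when the extra cases equal the objective cases. This is an identity and not an estimate: the protocol gives no reinfection or symptom rates to put into it. Pattern counts do not supply them either, since the patterns are not equally likely.

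**What a laboratory requirement would miss.** Among truly reinfected symptomatic subjects, the share with no positive test is (1 − 0.70w)(1 − m). Here 0.70 = 1 − 0.30 follows from the PCR false-negative rate of about 30% in the Rationale, w is the share who have a PCR, and m is the IgM sensitivity. The protocol gives neither w nor m, so both are assumed. Test errors are taken as independent, and blood as drawn in every episode.

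| m (assumed) | w = 1 | w = 0.5 | w = 0 |
|---|---|---|---|
| 0.9 | 0.30 × 0.1 = 3% | 0.65 × 0.1 = 6.5% | 1 × 0.1 = 10% |
| 0.5 | 0.30 × 0.5 = 15% | 0.65 × 0.5 = 32.5% | 1 × 0.5 = 50% |
| 0.2 | 0.30 × 0.8 = 24% | 0.65 × 0.8 = 52% | 1 × 0.8 = 80% |

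The low value of m is included because the Rationale says antibodies are known to be detectable from the second week after onset, with recent reports from day 4. Blood drawn at the first symptoms may come too early.

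**The case against.** The best defence is that the criterion is deliberately sensitive. Study RT-PCR reaches only symptomatic inpatients of a Covid unit, so staff and outpatients depend on community tests reported by questionnaire. PCR misses about 30%, and early blood may be antibody-negative. A rule that insists on a test could lose many real reinfections. The criterion is also the formal definition, while the objective carries only a bracketed explanation, and the two rules are nested rather than mutually exclusive.

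Much of this stands, and it is why the loss is shown above. It does not remove the contradiction. If the broad rule was intended, the objective describes something else, and nothing in the protocol says that the criterion prevails. Nested rules still classify the same subject differently. The test-positive route without symptoms may well be intended, since WP 2 also counts asymptomatic infections, but that does not explain the symptom-only route.

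A reader might infer more than the text supports:

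- *That the denominator contradicts the criterion.* It requires laboratory evidence of an infection, whereas the numerator concerns a later episode. A looser standard for the second episode is a possible design choice.
- *That symptom-only episodes are mainly test-negative or overlooked.* With study RT-PCR so restricted, many may simply have had no PCR.
- *That the WP 1 rule is a third contradiction.* It serves a separate objective in a stated IgG subgroup. The counts are not directly comparable, but that is not an error.

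**Conclusion.** The concern holds: WP 2 fixes the same reinfection frequency by two different rules, and recurrent symptoms without laboratory evidence count under one and not the other, however the objective is read. The criterion counts 7 of 8 patterns against 3, or 5 on the alternative reading, so the figure of 3 should not be quoted as the only one.

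The direction is certain only with the interval condition set aside and a common denominator: the criterion's frequency is then equal or higher. It is tempting to go on and claim inflation by some multiple. The document gives no rates from which to derive one, and any such figure would only restate the rates assumed.

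The consequence is limited. This is a descriptive secondary result with no test or sample size resting on it, and symptoms, PCR and IgM are collected separately, so either rule can be applied later. It should still be corrected, because the protocol states the rule twice and differently.

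**What to change.** Reconcile the WP 2 objective and the WP 2 criterion, using the same words in both places:

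1. State one rule for the main WP 2 reinfection frequency that requires laboratory evidence, worded so that the grouping of symptoms, PCR and IgM cannot be read two ways.
2. Say in both places whether asymptomatic test-positive episodes count. If they do not, the rule is S and (P or I), 3 of 8 patterns; if they do, it is P or I, 6 of 8.
3. Say in both places whether the symptom-free interval applies.
4. Report symptom-only episodes on a separate line as suspected reinfections, outside the main frequency.
5. Note that the WP 1 count uses its own confirmed definition in the IgG subgroup.

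Requiring laboratory evidence follows the natural reading of the objective and is in line with the WP 1 definition. The change is to wording only and needs no new data. The price is fewer counted events: untested or false-negative reinfections would appear only as suspected. Under the assumptions shown, that share runs from 3% to 80% of symptomatic reinfections, depending mainly on access to PCR and the timing of blood sampling. It could be large, so the suspected line should be published beside the main frequency.
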